# Appendix A

19c Evidence of hepatic disease as determined by any one of the following: aspartate aminotransferase or alanine aminotransferase values exceeding 2x upper limit of normal at Visit 1, history of hepatic encephalopathy, history of oesophageal varices, or history of porto-caval shunt	
Measured from the start of all available data of drug initiation in any diagnosis position in inpatient and outpatient care setting
 
Hepatic Encephalopathy/Coma ICD-9 diagnosis: 070.0, 070.2x, 070.4x, 070.6, 070.71, 572.2 ICD-10 diagnosis: B15.0, B16.0, B16.2, B17.11, B19.0, B19.11, B19.21, K72.90, K72.91
 
Esophageal Varices ICD-9 diagnosis: 456.0, 456.1, 456.2x, 572.3 ICD-10 diagnosis: I85.xx, K76.6
 
Porto-Caval Shunt ICD-9 procedure: 39.1, 42.91 ICD-10 procedure: Codes are in the sheet 'PCShunt' CPT-4 code: 37182, 37183, 37241
 
Cirrhosis/Chronic Hepatic Diseases ICD-9 diagnosis: 571.0, 571.2, 571.3, 571.4, 571.5, 571.6 ICD-10 diagnosis: K70.0, K70.30, K70.9, K73.0, K73.2, K73.8, K73.9, K75.4, K74.0, K74.60, K74.69, K74.3, K74.4, K74.5, K74.1
 
NASH ICD-9 diagnosis: 571.8, ICD-10 diagnosis: K76.0
	
19d Current treatment with cholestyramine or colestipol resins	OR the following:	
20 Presence of any other disease with a life expectancy of 5 years	Measured 30 days prior to and including the day of index drug initiation for oral generic prescription claims of  Cholestyramine, Colestipol, Colesevelam	
21 Any Ivabradine use -- Approved in April 2015 (same year as Entresto)	Charlson Comorbidity Index > 10  Measure since 2015/all available data in drug prescription claims for any dispensings of  Generic name: Ivabradine Brand name: Corlanor	

# Appendix A

	Variable	Codes and Medications (all medical claims, inpatient and outpatient should be used to define the conditions unless otherwise specified)	Coefficients ("Score")	When Measured for replicating	When Measured ([name]'s algorithm)
1	Intercept	N/A	-1.37219		
2	Cardiomyopathy	ICD-9 diagnosis: 425.x ICD-10 diagnosis: I42.x, I43.x	1.415113	Measured 180 days prior to and including the date of index drug initiation	6 months prior to index date + index date + 30days post-index
3	Diastolic heart failure	ICD-9 diagnosis: 428.3x (not co-occurring with 428.2x ) ICD-10 diagnosis: I50.3x (not co-occurring with I50.2x)	-0.950856	Measured between 180 days prior to and including the date of drug initiation and pick claim closest to the index initiation	on index date
4	Left heart failure	ICD-9 diagnosis: 428.1x (not co-occurring with more specific systolic or diastolic HF codes of 428.2x or 428.3x) ICD-10 diagnosis: I50.1 (not co-occurring with more specific systolic or diastolic HF codes of I50.2x or I50.3x)	0.766415	Measured between 180 days prior to and including the date of drug initiation and pick claim closest to the index initiation	on index date
5	Systolic heart failure	ICD-9 diagnosis: 428.2x (not co-occurring with 428.3x) ICD-10 diagnosis: I50.2x (not co-occurring with I50.3x)	0.754954	Measured between 180 days prior to and including the date of drug initiation and pick claim closest to the index initiation	on index date
6	Myocardial infarction	ICD-9 diagnosis: 410.xx ICD-10 diagnosis: I21.01, I21.02, I21.09, I21.11, I21.19, I21.21, I21.29, I21.3, I21.4, I22.0, I22.1, I22.2, I22.8, I22.9	0.651778	Measured 180 days prior to and including the date of index drug initiation	6 months prior to index date + index date + 30days post-index
7	Unspecified heart failure	ICD-9 diagnosis: 428.0x, 428.4x, 428.9x, 428.2x PLUS 428.3x ICD-10 diagnosis: I50.4x, I50.8x, I50.9, I50.2x PLUS I50.3x	-0.577221	Measured between 180 days prior to and including the date of drug initiation and pick claim closest to the index initiation	on index date
8	Number of hospitalizations for CHF	ICD-9 diagnosis: 428.x, 398.91, 402.01, 402.11, 402.91, 404.01, 404.11, 404.91, 404.03, 404.13, 404.93 ICD-10 diagnosis: I50.1, I50.2x, I50.4, I50.814, I09.81, I11.0, I13.0, I13.2	0.346289	Measured 180 days prior to and including the date of index drug initiation	6 months prior to index date (including index date)
9	Male gender	Male	0.323651	Measured on the date of index drug initiation	on index date
10	Implantable cardioverter defibrillator	ICD-9 diagnosis: V45.02 ICD-10 diagnosis: Z95.810 ICD-9 procedure: 37.94 - 37.98 ICD-10 procedure: Please copy from ICD-10 codes tabs for implantable cardioverter defibrillator	0.275032	Measured 180 days prior to and including the date of index drug initiation	6 months prior to index date + index date + 30days post-index

# Appendix A

11	ACE inhibitor	Prescription claims for: Benazepril, captopril, enalapril, fosinopril, lisinopril, moexipril, perindopril, quinapril, ramipril, trandolapril	0.221748	Measured 180 days prior to and including the date of index drug initiation	6 months prior to index date + index date + 30days post-index
12	Index diagnosis recorded during an outpatient visit	Any diagnosis position in an outpatient care setting ICD-9 diagnosis: 428.x, 398.91, 402.01, 402.11, 402.91, 404.01, 404.11, 404.91, 404.03, 404.13, 404.93 ICD-10 diagnosis: I50.1, I50.2x, I50.4x, I50.814, I09.81, I11.0, I13.0, I13.2	-0.187191	Measured between 180 days prior to and including the date of drug initiation and pick claim closest to the index initiation	on index date
13	Mineralocorticoid receptor antagonist	Prescription claims for: Eplerenone, spironolactone	0.166008	Measured 180 days prior to and including the date of index drug initiation	6 months prior to index date + index date + 30days post-index
14	Anemia	ICD-9 diagnosis: 280.xx - 285.xx ICD-10 diagnosis: Please copy from ICD-10 codes tabs for anemia	-0.165353	Measured 180 days prior to and including the date of index drug initiation	6 months prior to index date + index date + 30days post-index
15	Valve disorder	ICD-9 diagnosis: 394.x - 397.x, 398.9x, V42.2, V43.3 ICD-10 diagnosis: Please copy from ICD-10 codes tabs for valve disorder ICD-9 procedure: 35.1x, 35.2x ICD-10 procedure: Please copy from ICD-10 codes tabs for valve disorder CPT code: 33660-33665, 33400-33403, 33420-33430, 33460, 33463-33468, 33475, 33496, 0257T, 0258T, 0259T, 0262T	-0.163684	Measured 180 days prior to and including the date of index drug initiation	6 months prior to index date + index date + 30days post-index
16	Digoxin	Prescription claims for: Digoxin	0.163224	Measured 180 days prior to and including the date of index drug initiation	6 months prior to index date + index date + 30days post-index
17	Thiazide diuretic	Prescription claims for: Bendroflumethiazide, Benztiazide, Chlorothiazide, Chlorthalidone, Hydrochlorothiazide, Indapamide, Methyclothiazide, Metolazone, Polythiazide, Quinethazone, Trichlormethiazide	-0.160819	Measured 180 days prior to and including the date of index drug initiation	6 months prior to index date + index date + 30days post-index
18	Obesity	ICD-9 diagnosis: 278.00, 278.01, V85.3x, V85.4x ICD-10 diagnosis: E65.x, E66.x, E67.x, E68.x CPT codes: 43842, 43843, 43846, 43847, 43848, G0447 Prescription claims for: orlistat, sibutramine, phentermine, benzphetamine, phendimetrazine, diethylpropion	-0.141956	Measured 180 days prior to and including the date of index drug initiation	6 months prior to index date + index date + 30days post-index
19	Nitrate	Prescription claims for: Nitroglycerin, isosorbide dinitrate, isosorbide mononitrate, ranolazine	0.129225	Measured 180 days prior to and including the date of index drug initiation	6 months prior to index date + index date + 30days post-index
20	Other dysrhythmias	ICD-9 diagnosis: 427.0x, 427.1x, 427.2x, 427.4x, 427.6x, 427.8x, 427.9x, 785.0x ICD-10 diagnosis: Please copy from ICD-10 tab for other dysrhythmias	0.116652	Measured 180 days prior to and including the date of index drug initiation	6 months prior to index date + index date + 30days post-index
21	Hypertension	ICD-9 diagnosis: 401.xx, 402.xx, 405.xx ICD-10 diagnosis: I10, I11.0, I11.9, I12.0, I12.9, I13.0, I13.10, I13.11, I13.2, I15.0, I15.1, I15.2, I15.8, I15.9	-0.098539	Measured 180 days prior to and including the date of index drug initiation	6 months prior to index date + index date + 30days post-index

# Appendix A

22	Beta blocker	Prescription claims for oral: Acebutolol, atenolol, betaxolol, bisoprolol, carteolol, carvedilol, labetalol, metoprolol, nadolol, nebivolol, penbutolol, pindolol, propranolol	0.087257	Measured 180 days prior to and including the date of index drug initiation	6 months prior to index date + index date + 30days post-index
23	Loop diuretic	Prescription claims for oral: Bumetanide, furosemide, torsemide, ethacrynic acid	0.084251	Measured 180 days prior to and including the date of index drug initiation	6 months prior to index date + index date + 30days post-index
24	Rheumatic heart disease	ICD-9 diagnosis: 393 - 398.x ICD-10 diagnosis: I05.xx - I09.xx	-0.073889	Measured 180 days prior to and including the date of index drug initiation	6 months prior to index date + index date + 30days post-index
25	Psychosis	ICD-9 diagnosis: 290.8x, 290.9x, 295.xx, 297.xx, 298.xx, 299.xx, 780.0x - 780.5x ICD-10 diagnosis: Please copy from ICD-10 tab for Psychosis	-0.068198	Measured 180 days prior to and including the date of index drug initiation	6 months prior to index date + index date + 30days post-index
26	Coronary artery bypass graft	ICD-9 procedure: 36.1x, 36.2x ICD-10 procedure: Please copy from ICD-10 tab for CABG CPT code: 33510 – 33536, 33545, 33572	-0.040175	Measured 180 days prior to and including the date of index drug initiation	6 months prior to index date + index date + 30days post-index
27	COPD	ICD-9 diagnosis: 491.xx, 492.xx, 496.xx, 493.2x ICD-10 diagnosis: J41.x, J42.x, J43.x, J44.x	-0.037023	Measured 180 days prior to and including the date of index drug initiation	6 months prior to index date + index date + 30days post-index
28	Sleep apnea	ICD-9 diagnosis: 327.2x, 780.51, 780.53, 780.57 ICD-10 diagnosis: G47.3x	-0.03556	Measured 180 days prior to and including the date of index drug initiation	6 months prior to index date + index date + 30days post-index
29	Hypertensive nephropathy	ICD-9 diagnosis: 403.xx, 404.xx ICD-10 diagnosis: I12.x, I13.xx	-0.03383	Measured 180 days prior to and including the date of index drug initiation	6 months prior to index date + index date + 30days post-index
30	Depression	ICD-9 diagnosis: 293.83, 296.2x, 296.3x, 296.9x, 298.0x, 300.4x, 309.1x, 309.28, 311.xx ICD-10 diagnosis: F06.3x, F32.x, F33.x, F34.x, F39.x, F43.21, F43.23	-0.033829	Measured 180 days prior to and including the date of index drug initiation	6 months prior to index date + index date + 30days post-index
31	Hypotension	ICD-9 diagnosis: 458.xx ICD-10 diagnosis: I95.x	-0.017282	Measured 180 days prior to and including the date of index drug initiation	6 months prior to index date + index date + 30days post-index
32	Stable angina	ICD-9 diagnosis: 413.xx ICD-10 diagnosis: Please copy from ICD-10 tab for stable angina	-0.015657	Measured 180 days prior to and including the date of index drug initiation	6 months prior to index date + index date + 30days post-index
33	Age	Continous	-0.005747	Measured on the date of index drug initiation	on index date

## Appendix A

34	Atrial fibrillation	ICD-9 diagnosis: 427.3x ICD-10 diagnosis: I48.x	-0.002267	Measured 180 days prior to and including the date of index drug initiation	6 months prior to index date + index date + 30days post-index
35	Hyperlipidemia	ICD-9 diagnosis: 272.xx ICD-10 diagnosis: E78.xx	-0.001805	Measured 180 days prior to and including the date of index drug initiation	6 months prior to index date + index date + 30days post-index

## Appendix A

### Mortality- Dependent on data source.

#### 1. All-cause mortality / inpatient mortality

Identified using the vital status file-

Medicare

Identified using the discharge status codes-

Optum-

- 20 = EXPIRED
- 21 = EXPIRED TO BE DEFINED AT STATE LEVEL
- 22 = EXPIRED TO BE DEFINED AT STATE LEVEL
- 23 = EXPIRED TO BE DEFINED AT STATE LEVEL
- 24 = EXPIRED TO BE DEFINED AT STATE LEVEL
- 25 = EXPIRED TO BE DEFINED AT STATE LEVEL
- 26 = EXPIRED TO BE DEFINED AT STATE LEVEL
- 27 = EXPIRED TO BE DEFINED AT STATE LEVEL
- 28 = EXPIRED TO BE DEFINED AT STATE LEVEL
- 29 = EXPIRED TO BE DEFINED AT STATE LEVEL
- 40 = EXPIRED AT HOME (HOSPICE)
- 41 = EXPIRED IN A MEDICAL FACILITY (HOSPICE)
- 42 = EXPIRED - PLACE UNKNOWN (HOSPICE)

Truven-

- 20 - Died
- 22 - Died
- 23 - Died
- 24 - Died
- 25 - Died
- 26 - Died
- 27 - Died
- 28 - Died
- 29 - Died
- 40 - Other died status or Expired at home (Hospice claims only) (depends on year)
- 41 - Other died status or Expired in medical facility (Hospice claims only) (depends on year)
- 42 - Other died status or Expired - place unknown (Hospice claims only) (depends on year)
- 21 - Died or Disch./Transf. to court/law enforcement (depends on year)

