### 6.3 Outcome variables and study follow-up:

#### 6.3.1 Outcome variables

Effectiveness outcome variables of interest (definitions provided in **Appendix A**):

- **Primary outcome:** Composite of hospitalization for heart failure and all-cause mortality
- Secondary outcomes:
  - Heart failure hospitalization
  - All-cause death

Control outcomes of interest (control outcomes only serve to assess aspects of study validity but are not further interpreted, definitions provided in Appendix A):

1. Bleeding (we expect to see a null association, as renin angiotensin aldosterone inhibitors are not expected to have any impact on this outcome)

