# Appendix A

#	PARADIGM-HF trial definitions	Implementation in routine care	Please see the following Google Drive for further details or any missing information : https://drive.google.com/drive/folders/1WD618wrywJjeXzfLTcuk-VCcnb6b-gV	
Trial details - active comparison - 2 weeks run-in			ICD-10 codes are not listed in this document because of excel cell size limitations and excessive number of ICD-10 codes. Full ICD-10 code lists will be available in the above Google Drive Folder (link above). ICD-9 to ICD-10 code conversions were completed using a SAS macro that implements forward/ backward mapping based on the CMS ICD-9 to ICD-10 mapping: https://www.nerb.org/data/icd9-icd-10-cm-and-pcs-crosswalk-general-equivalence-mapping.html	
EXPOSURE vs. COMPARISON		References/Rationale		Color coding
LCZ696 (sacubitril/valsartan) 200 mg twice daily vs. enalapril 10 mg twice daily  Aim: To determine if LCZ696 is superior to enalapril in reducing the risk of death and of hospitalization for HF		Exposure: new-use of sacubitril/valsartan Reference: enalapril		Criteria Adequate mapping in claims
PRIMARY OUTCOME				

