The primary outcome is a composite of death from cardiovascular causes or hospitalization for heart failure		
Measured 14 days after drug initiation in diagnosis position specified below and inpatient care setting:
 
Hospital admission for CHF (Inpatient only, any position)
 
ICD-9 diagnosis: 428.x, 398.91, 402.01, 402.11, 402.91, 404.01, 404.11, 404.91, 404.03, 404.13, 404.93
 
ICD-10 diagnosis: I50.1, I50.2x, I50.4, I50.81, I09.81, I11.0 (hypertensive heart disease with HF), I13.0 (hypertensive heart and chronic kidney disease with HF and stage 1 through stage 4 CKD), I13.2 (hypertensive heart and CKD with HF and with stage 5 CKD or ESRD)
 
CV death
 
Inpatient mortality - heart failure --
 
Mortality- Dependent on data source.
 
 
CV mortality
 
Information on CV mortality through data linkage with the National Death Index (NDI) will be available for Medicare and Optum Clininformatics.
 
All-cause inpatient mortality
 
 
Identified using the discharge status codes- Optum-
 
 
• 20 = EXPIRED
 
• 21 = EXPIRED TO BE DEFINED AT STATE LEVEL
 
• 22 = EXPIRED TO BE DEFINED AT STATE LEVEL
 
• 23 = EXPIRED TO BE DEFINED AT STATE LEVEL
 
• 24 = EXPIRED TO BE DEFINED AT STATE LEVEL
 
		Intermediate mapping in claims
INCLUSION CRITERIA				Poor mapping or cannot be measured in claims
1	Age ≥ 18 years	Age 18 years or older at drug initiation		Can't be measured in claims but not important for the analysis
2	NYHA functional class II-IV	
Measured 45 days prior to and including the day of oral drug initiation in generic prescription claims requiring 28 days supply of Loop or Thiazide diuretics
 
Loop Diuretics: Bumetanide, Furosemide, Torsemide, Ethacrynic acid
 
-OR-
 
Thiazide and Thiazide-like Diuretics: Hydrochlorothiazide, Chlorothiazide, Chlorthalidone, Indapamide, Metolazone, Cyclothiazide, Hydroflumethiazide, Bendroflumethiazide, Benztiazide, Methyclothiazide, Polythiazide
		

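### Appendix A does not give one consistent definition of the all-cause death component, and its MarketScan list counts a status code as death that can also mean a live discharge

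*Protocol*

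**What the plan says.** Protocol Section 6.3.1 gives the primary outcome as "Composite of hospitalization for heart failure and all-cause mortality", lists all-cause death as a secondary outcome, and refers to Appendix A for definitions. Appendix A deals with death in two places.

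- **Primary outcome row.** The row opens with a lead-in that fixes an inpatient care setting. Death comes under a cardiovascular-death label. The items named are cardiovascular mortality, a linkage statement ("Information on CV mortality through data linkage with the National Death Index (NDI) will be available for Medicare and Optum Clininformatics") and "All-cause inpatient mortality". Optum discharge status codes follow, and the last one printed is "24 = EXPIRED TO BE DEFINED AT STATE LEVEL". No Medicare or MarketScan rule is printed.
- **Mortality sheet.** Its item 1 is titled as all-cause and inpatient mortality together. Medicare deaths come from the vital status file. Optum deaths come from discharge status 20-29 and 40-42, including "40 = EXPIRED AT HOME (HOSPICE". The Truven list uses the same code numbers but qualifies one of them: "21 - Died or Disch./Transf. to court/law enforcement (depends on year". The Optum entry for that code reads "21 = EXPIRED TO BE DEFINED AT STATE LEVEL".

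The Truven block is read here as MarketScan, the only data source in Section 3 not otherwise covered on that sheet.

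**The concern.** Death is half of the composite by definition and the whole of one secondary outcome, so the plan should leave no doubt about which deaths count. Two points are open.

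First, a death at home or at an unknown place under hospice cannot be an inpatient death. An analyst who follows the wording of the primary outcome row would leave out patients carrying those codes, and one who follows the mortality sheet would count them. These are deaths that the heart-failure-admission component cannot pick up. If they are not events, follow-up ends under another rule in Section 6.3.2, such as end of registration or drug discontinuation plus the grace period. The patient is then censored because of the event under study.

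Second, as the Truven list is written, a MarketScan patient discharged alive with status 21 in a year when the code carries that meaning is scored as dead, and follow-up stops there.

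**Working it through.** **1. The texts side by side**

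| | Section 6.3.1 | Appendix A, primary outcome row | Appendix A, mortality sheet |
|---|---|---|---|
| Cause | All causes | Cardiovascular label; then cardiovascular and all-cause items | All causes |
| Setting | Not restricted | Inpatient | Title names both; hospice codes include home and unknown place |
| Medicare | Not stated | Death Index linkage, cardiovascular | Vital status file |
| Optum | Not stated | Death Index linkage, cardiovascular; status 20-24 printed | Status 20-29, 40-42 |
| MarketScan | Not stated | Nothing printed | Status 20-29, 40-42; 21 year-dependent |

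The conflict lies in the cause and setting rows. It does not depend on the length of the printed Optum list.

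**2. Status 21.** Codes 40-42 in the Truven list also vary by year, but both of their meanings are deaths. Only 21 has a live meaning. MarketScan data run from July 2015 to December 2018 (Section 5.2.1), so a rule is needed for those years only.

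**3. Reproducing the plan's power.** Inputs from the Final Power Assessment: 3,033 matched patients per group, risk 215.25 per 1,000, HR 0.8, two-sided alpha 0.05.

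- Events: 2 × 3,033 × 0.21525 = 1,305.7, as stated.
- Power: Φ(|ln 0.8| × √1,305.7 / 2 − 1.96) = Φ(2.07) = 0.981, as stated (0.98085).

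**4. A bound for the composite.** The Section 9 censoring table shows 150 deaths (64 + 86) among 6,066 matched patients, 2.47%, not split by database or code. Assume all 150 are among the expected events and that a narrower definition loses a share of them:

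| Share of the 150 lost | Pooled power |
|---|---|
| 10% | 0.980 |
| 25% | 0.978 |
| 50% | 0.975 |
| 100% | 0.967 |

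**5. An illustration for all-cause death.** Two assumptions are needed, and neither is in the documents:

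- 40-67% of the deaths are in Optum and MarketScan. The upper end is their share of matched pairs, (1,279 + 748) / 3,033 = 67%.
- 10-40% of those deaths carry codes 40-42.

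Then:

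- Deaths that move: 0.40 × 0.10 × 150 = 6, to 0.67 × 0.40 × 150 = 40. That is 4-27% of 150.
- SE of the log HR, 2/√deaths: 2/√150 = 0.163 becomes 2/√144 = 0.167 to 2/√110 = 0.191.
- Share of pooled expected composite events: 6/1,306 = 0.5% to 40/1,306 = 3.1%, and less where a heart-failure admission came first.

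The subtraction also assumes that the 150 deaths were counted with the broader list, which the protocol does not say.

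**The case against.** The strongest objection is that the difference in code lists is a printing artefact. The primary outcome row prints the first five Optum codes in the same order and wording as the mortality sheet and then stops, without the Medicare and MarketScan parts. Appendix A itself says "Please see the following Google Drive for further details or any missing information" and mentions spreadsheet cell limits, although only for ICD-10 codes. This stands. A reader might infer that status 20-24 is a rival Optum definition, but the documents do not support that: the shorter list is probably a cut-off copy.

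It can also be said that the inpatient lead-in is phrased for diagnosis codes, and that the mortality sheet carries the word inpatient in its own title while listing the hospice codes. Loose labelling is therefore a fair description of part of the problem. But the outcome row also names the death item itself as inpatient, and a title that joins two different endpoints does not say which is meant.

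Third, linkage to the National Death Index could recover out-of-hospital cardiovascular deaths in Optum. That is so if it is used, but it is described for cardiovascular mortality only, it does not cover MarketScan, and the protocol does not say how it enters an all-cause outcome.

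On status 21, the list already flags the year dependence, and which years carry the live meaning cannot be seen from the documents. So false deaths are possible but not shown. The flag is not a rule, however.

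**Conclusion.** The point holds: Section 6.3.1 asks for all-cause mortality, and Appendix A gives labels that disagree on cause and setting and a MarketScan code that can misclassify a living patient. It should be settled before outcomes are analysed.

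Its reach is limited. On the mortality sheet, Medicare deaths come from the vital status file, so neither code-list question touches them there. The live meaning of status 21 is documented for MarketScan only. A reader might extend it to Optum, but the Optum entry gives that code as expired and nothing else. A reader might also infer that the outcome row governs the primary composite and the mortality sheet the secondary outcome. Nothing assigns them that way, since Section 6.3.1 sends all outcomes to Appendix A as a whole.

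The size cannot be computed from the documents. Under the stated assumptions, 6-40 deaths would move: 0.5-3% of pooled expected composite events, but 4-27% of recorded deaths. The concern therefore bears mainly on the all-cause-death outcome. It is not a power problem, since pooled power stays at about 0.967 or higher even in the extreme case. Status 21 probably affects few patients.

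**What to change.** State one all-cause death definition per database and use it for both the composite and the secondary outcome:

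- **Medicare:** the vital status file.
- **Optum and MarketScan:** the discharge status codes on the mortality sheet, including 40-42.
- **MarketScan status 21:** drop it, or count it only in data years for which the database dictionary defines it as died.

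Have the primary outcome row refer to this definition, without the cardiovascular-death and inpatient labels on the death component. Say explicitly whether, where and for which outcome deaths linked from the National Death Index are used. Simply replacing the text of the row with the code list would remove the linkage provision without a decision having been made.

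The cost is a wording change, a small edit to the outcome code list and a look-up in the MarketScan dictionary. No new data are needed unless linkage is chosen. The death count may change slightly, so the change should be made and dated before the outcome analysis is run.
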